Aim 1: To adapt DBT skills training for patients with metastatic lung cancer (DBT-MLC). We will conduct focus groups and in-depth interviews with key stakeholders: patients with metastatic lung cancer (N=20, 4-6 groups), thoracic oncology providers (N=6), and clinicians with expertise in survivorship and behavioral symptom management (N=6), to collect input on the format and content of DBT skills training (i.e., delivery, dose, materials). Stakeholder input will inform adaptation to increase relevance and acceptability to patients with metastatic lung cancer. This will inform production of an initial DBT-MLC protocol (i.e., manualized protocol, patient workbook). Topical experts (N=5) with specialization in areas relevant to DBT-MLC (DBT, intervention science) will provide detailed feedback on the developed DBT-MLC protocol. Feedback will be integrated to produce the next iteration of the DBT-MLC protocol. *H1*: The systematic steps of the ADAPT-ITT framework will produce an adapted version of DBT skills training that can be implemented with metastatic lung cancer patients (DBT-MLC).

Aim 2: To pilot test and refine the developed DBT-MLC protocol, "LiveWell". Participants will be metastatic lung cancer patients who score >3 on the NCCN distress thermometer. We will evaluate feasibility, acceptability, examine pre- to post- intervention outcomes, and conduct qualitative exit interviews to collect participants' experience and feedback. We hypothesize that DBT-MLC will demonstrate evidence of: *H1*: feasibility (meet study accrual, >80% completed sessions, <25% attrition); *H2*: acceptability (>80% of participants report satisfaction); *H3*: benefit in the primary outcome of psychological distress (i.e., depression, anxiety); *H4*: benefit on secondary outcomes (fatigue, dyspnea, pain, emotion regulation, tolerance of uncertainty, quality of life, illness acceptance, DBT skill use). *H5*: Information collected in qualitative exit interviews will inform DBT-MLC refinement.

Background & Significance

• Should support the scientific aims of the research

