We will assess the feasibility, acceptability, and pre-to-post intervention improvement in outcome variables using a single-arm pilot study (N=30). Standardized self-report assessment measures will be administered at baseline, immediately post-intervention, and 1 month follow-up. Participants can complete assessments via hard copy or online via RedCap. All participants will be offered participation in an exit interview to inform DBT-MLC refinement. If necessary and appropriate, patient participants in Phase II of the study may be provided with a device (e.g., tablet computer) to participate in the pilot intervention program. A data plan will be provided if necessary. These will be set with restrictions. Participants will return tablet computers following completion of study activities.

Study personnel will be trained in procedures related to delivering DBT-MLC. [name] will attend formal trainings in delivering DBT skills training as part of the fellowship project. She will create a standard operating procedure manual for the delivery of DBT-MLC. Study interventionists will thoroughly review the treatment manual and rehearse intervention delivery by role playing skills training sessions.

• List inclusion/exclusion criteria and how subjects will be identified.

Eligibility criteria for patients. Eligibility criteria for patients were determined in consultation with mentor and thoracic oncologist, [name], MD, and based on previous psychosocial studies in advanced lung cancer.

Eligibility criteria for patients included in Phase I and Phase II include:

- 1) be diagnosed with metastatic (AJCC stage IV) non-small cell lung cancer,
- 2) be undergoing systemic treatment (chemotherapy, targeted therapy, and/or immunotherapy) for lung cancer at DCI.
- 3) score \geq 3 on the National Comprehensive Cancer Network Distress Thermometer for distress over the past week (Range: 0-10),
- 4) be > 18 years of age,
- 5) be able to understand, speak, and read English, and
- 6) be able to provide informed consent.

Exclusion criteria for patients include:

- 1) reported or suspected cognitive impairment subsequently informed by a Montreal Cognitive Assessment (MOCA) of <26;
- 2) presence of untreated serious mental illness (e.g., schizophrenia) indicated by the medical chart, treating oncologist, or other medical provider; or
- 3) expected survival of 4 months or less.

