• If not already presented in #4 above, describe study-related treatment or use of an investigational drug or biologic (with dosages), or device, or use of another form of intervention (i.e., either physical procedures or manipulation of the subject or the subject's environment) for research purposes.

The primary (psychological distress) and secondary outcome measures (fatigue, dyspnea, pain, emotion regulation, tolerance of uncertainty, DBT skills use) will be collected at all three assessment time points. We selected brief measures to reduce patient burden. It is estimated that assessments will take approximately 20-30 minutes to complete.

- a. Sociodemographic, clinical, and lifestyle variables. Baseline assessment will include relevant sociod emographic variables (e.g., age, race, ethnicity, employment, education). Clinical information (e.g., date of cancer diagnosis, date(s) and type(s) of treatment) will be collected via medical record review. Participants will self-report lifestyle characteristics (e.g., cigarette smoking, alcohol consumption).
- **b. Feasibility.** Treatment feasibility will be assessed through analysis of study process data, including study accrual (goal met in the allotted time frame), session attendance (\geq 80%), and treatment attrition (\leq 25%). Reasons for missed sessions and study discontinuation will be collected.
- c. Acceptability. Acceptability will be assessed post-intervention using the 8-item Client Satisfaction Questionnaire (CSQ). The scale includes eight items assessing participants' level of satisfaction with treatment, with response options ranging from 1 (quite dissatisfied) to 4 (very satisfied). Acceptability will be demonstrated by 80% of participants reporting intervention satisfaction on the CSQ. Intervention engagement will be assessed on an ongoing basis and recorded in RedCap (i.e., homework completion).

d. Pre- to Post-Intervention Outcomes.

Psychological Distress. Distress will be measured using the PROMIS Depression (8 items) and Anxiety (8 items) Short Form Scales. Participants are asked to rate how frequently they experienced each symptom over the past 7 days on a 5-point scale ranging from 1 (never) to 5 (always), with higher scores indicating greater distress (i.e., more depression or anxiety). PROMIS measures of distress have demonstrated reliability and validity in cancer samples as well as sensitivity to change in patients participating in psychological interventions.

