iv. Aim 2: Test and Refine Intervention. Descriptive statistics (frequencies, mean, median, standard deviation) will be used to examine feasibility (i.e., \geq 80% of sessions completed, attrition \leq 25%) and acceptability (i.e., \geq 80% participants report satisfaction on CSQ). Paired sample t-tests will be run to quantify the degree of change over time for the primary and secondary intervention outcomes. Effect sizes will be computed using Cohen's d. Unconditional latent growth models will be used to assess main time effects across baseline, immediately post-treatment and 1 month post-treatment. Time will be coded as the number of weeks since the baseline assessment. Control variables and their interactions with time will be included in conditional models. Analyses will be conducted using an intent-to-treat approach to include all available data (N=up to 38). Exit interviews will be coded and analyzed using methods similar to those described under Aim 1. Themes and feedback that are uncovered through exit interviews will be used to inform intervention refinement.

Data & Safety Monitoring

• Summarize safety concerns, and describe the methods to monitor research subjects and their data to ensure their safety, including who will monitor the data, and the frequency of such monitoring. If a data monitoring committee will be used, describe its operation, including stopping rules and frequency of review, and if it is independent of the sponsor (per 45 CFR 46.111(a) (6)).

The proposed study carries minimal risk. The protocol does not use an investigational drug, procedure, or device. Data obtained from participants will include information from medical chart review, stakeholder interviews and focus groups, and self-report inventories. The study team considers the management of participant information and data as a key priority. Best practices for confidentiality and data management will be observed. Two password protected databases will be used for this study to ensure confidentiality.

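### Does the plan need changing because the distress cut-off and success thresholds carry strict signs in the summary text and inclusive signs in the operative text?

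*Combined protocol and SAP*

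**What the plan says.** The entry cut-off appears three times. The Research Abstract and Aim 2 (Objectives & hypotheses to be tested) use the same sentence: "Participants will be metastatic lung cancer patients who score >3 on the NCCN distress thermometer". The third statement is item 3 of the patient eligibility list in Design & Procedures: "score \geq 3 on the National Comprehensive Cancer Network Distress Thermometer for distress over the past week (Range: 0-10"). That list opens with "Eligibility criteria for patients included in Phase I and Phase II include", so it governs the pilot as well as the focus groups. No section comments on the difference.

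The pilot's success targets follow the same pattern. Aim 2 gives H1 as "feasibility (meet study accrual, >80% completed sessions, <25% attrition") and H2 as "acceptability (>80% of participants report satisfaction"). Study Interventions, item b, gives "session attendance (\geq 80%), and treatment attrition (\leq 25"%). Item c of that section states the satisfaction target as a bare 80% with no sign. The Analytic Plan for Aim 2 gives "feasibility (i.e., \geq 80% of sessions completed, attrition \leq 25%) and acceptability (i.e., \geq 80% participants report satisfaction on CSQ").

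The Distress Thermometer is not among the outcome measures in Study Interventions. The primary outcome, psychological distress, is measured by the PROMIS Depression and Anxiety short forms.

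**The concern.** Entry criteria and success targets should read the same wherever they are stated. A reader of Aim 2 would take the pilot to be about patients scoring 4 or more, while a reader of the list would take it to be about patients scoring 3 or more. The screen is also a deliberate feature. The Background criticises earlier trials for not screening on distress at baseline, and the institutional monitors check that enrolled patients were eligible.

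The targets matter because the pilot's feasibility and acceptability results feed the decision on a larger randomized trial. If a result landed exactly on a target, the hypothesis in Aim 2 and the criterion in the analytic plan would give opposite answers, and the choice between them could be made after seeing the data.

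**Working it through.** The plan states no figure that depends on the cut-off, so there is none to reproduce. The check is to count what each sign admits.

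**Entry cut-off.** Input: range 0 to 10, from the eligibility list. Assumption: whole-number scores.

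- Strict, >3: scores 4 to 10, which is 7 values.
- Inclusive, ≥3: scores 3 to 10, which is 8 values.
- Difference: the score 3 only. No score qualifies under the strict sign and fails under the inclusive one.

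The documents do not give the frequency of a score of 3, so no patient count can be derived. A patient scoring 3 must still meet the other five inclusion criteria and none of the three exclusions.

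**Success targets.** Inputs: 8 sessions (Design & Procedures, Phase 2); about 30 participants with complete data and up to 38 recruited (Data management and attrition; Statistical Power). The signs differ only when target × denominator is a whole number.

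| Target | Denominator | Product | Inclusive sign | Strict sign |
|---|---|---|---|---|
| Satisfied, 80% | 30 | 24 | at least 24 | at least 25 |
| Satisfied, 80% | 38 | 30.4 | at least 31 | at least 31 |
| Attrition, 25% | 38 | 9.5 | at most 9 | at most 9 |
| Attrition, 25% | 30 | 7.5 | at most 7 | at most 7 |
| Sessions per patient, 80% | 8 | 6.4 | at least 7 | at least 7 |
| Sessions pooled, 80% | 30 × 8 = 240 | 192 | at least 192 | at least 193 |
| Sessions pooled, 80% | 38 × 8 = 304 | 243.2 | at least 244 | at least 244 |

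A satisfaction tie needs a number of responses divisible by 5, and an attrition tie needs a number enrolled divisible by 4. With 36 enrolled, for example, 0.25 × 36 = 9, so 9 losses pass the inclusive sign and fail the strict one. The count must also land exactly on the product. The plan does not define a pooled session denominator, so those two rows are illustrative.

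**Size of a tie.** With 30 responses, one participant is 1/30 = 3.3 percentage points. The standard error of an observed 80% is √(0.80 × 0.20 / 30) = 0.073, or 7.3 points. The gap between the two signs is less than half a standard error.

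**Pattern of the signs.** Four thresholds differ (distress, sessions, attrition, satisfaction), and every one goes from strict in the summary text to inclusive in the operative text. The age criterion directly below the distress item is also printed as a strict inequality, at 18 years, and again in the list for non-patient stakeholders. One typographic cause explains this pattern more simply than four separate design decisions.

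**The case for a change.** The strongest case for acting is that the contradiction is there in print and nothing resolves it. A lost underline is a guess: inclusive signs are printed correctly in the eligibility list, in Study Interventions and in the Analytic Plan, so they were not dropped throughout. The satisfaction tie falls at 30, the number the plan aims to have with complete data. Aligning a few signs would cost almost nothing.

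Most of this is fair. The wording does differ, and the documents cannot show whether the cause is typing or conversion. A tie at 24 of 30 is possible. What does not stand is that anyone would be misled in running or analysing the study. Staff screen against the eligibility list; an abstract and an aims paragraph are summaries and are not used to enrol anyone. The analyst works from the Analytic Plan, which agrees with Study Interventions on sessions and attrition and gives an explicit sign for satisfaction. The plan calls 30 approximate, and the intent-to-treat analysis uses up to 38, where no tie arises. The feasibility and acceptability results are descriptive, so a reader will see the count itself and can judge 24 of 30 without a sign.

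**Conclusion.** The signs differ as printed, but the point is clerical and calls for no change to the plan. It affects one screening score, 3, and the pass mark only when a result ties exactly with its target. It alters no sample size, test, outcome measure or assessment. The enrolled population is the one the eligibility list defines, and the targets to report against are those in the Analytic Plan. A routine baseline table of Distress Thermometer scores would show how many participants entered at 3. The signs can be checked against the source file and tidied whenever the text is next edited, but nothing in the study waits on that.

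This rests on three assumptions: scores are recorded as whole numbers, staff enrol from the eligibility list, and feasibility and acceptability are reported as counts with denominators. It takes no view on which cut-off is clinically preferable.

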For those who decline participation, information will immediately be deleted from our records including their address and telephone number. However, we will retain their name and MRN so that we do not contact a person who has already declined participation. This will allow us to respect the wishes of the patients who do not want to be involved. We will delete the patient's name and MRN upon completion of enrollment. We will retain demographic information and basic medical information on patients who decline in order to see if we are systematically under including certain subgroups of the study population, which would limit our ability to generalize findings. This information will always be kept separate from direct identifiers. If a patient is not eligible or if he/she decides he/she is not/no longer interested in participating, the patient will be provided with psychosocial resources offered through DCI, if needed. Participants will be told they can discontinue participation at any time with no impact to their medical care. Additionally, Duke patients with metastatic lung cancer are able to contact the study staff if they are interested in participating in this study. Participants will be compensated \$30 for participating in the focus group. Non-patient stakeholders who participate in interviews will be compensated with a \$20 Starbucks giftcard. Participants recruited into the single-arm pilot will be compensated \$40 for completing each of the three study assessments (i.e., baseline, post-intervention, 1-month follow-up, maximum compensation of \$120). We will conduct qualitative exit interviews with pilot participants to inform DBT-MLC intervention refinement. All participants will be offered the opportunity to participate in a qualitative exit interview after completing the post-intervention assessment. Qualitative exit interviews will follow similar procedures to the stakeholder interviews and participants will be compensated \$30.

Consent Process

• Complete the consent section in the iRIS Submission Form.

Subject's Capacity to Give Legally Effective Consent

• If subjects who do not have the capacity to give legally effective consent are included, describe how diminished capacity will be assessed. Will a periodic reassessment occur? If so, when? Will the subject be consented if the decisional capacity improves?

Only subjects who have capacity to give legally effective consent will be included in this study.

Study Interventions

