Tolerance of Uncertainty. The Intolerance of Uncertainty Scale (IUS) will be used to measure emotional, cognitive, and behavioral reactions to uncertainty situations. Participants indicate how characteristic 27 items are of them on a scale ranging from 1 (not at all characteristic of me) to 5 (entirely characteristic of me), with higher scores indicating greater intolerance of uncertainty. The IUS has demonstrated evidence of excellent reliability and validity in cancer samples.

Quality of Life. The Functional Assessment of Cancer Therapy - Lung Cancer version (FACT-L) will be used to assess quality of life across 5 domains (physical, emotional, social, functional, lung cancer-specific concerns).

Illness Acceptance. The Peace, Equanimity, and Acceptance in the Cancer Experience (PEACE) scale - Peaceful Acceptance of Illness sub scale will be used to assess illness acceptance.

DBT Skill Use. The DBT Ways of Coping Checklist (DBT-WCCL) – DBT Skills Subscale (DSS) will be used to assess patient-reported frequency of skill use to manage difficult situations. To avoid response bias, DBT language and the names of skills are avoided in the scale and general descriptions are used. Items are rated on a 0-3 scale, indicating if the coping strategy was never, rarely, sometimes, or regularly used in the past month when faced with a stressor. Items that are not aligned with skills that are included in DBT-MLC following study adaptation procedures (Phase 1) will be removed. The DSS has demonstrated evidence of reliability and validity, including criterion validity to accurately measure DBT skill use, in studies of patients undergoing DBT treatment.

e. Qualitative Exit Interviews. We will conduct qualitative exit interviews with pilot participants to inform DBT-MLC intervention refinement. All participants will be offered the opportunity to participate in a qualitative exit interview after completing the post-intervention assessment. Qualitative exit interviews will follow similar procedures to the stakeholder interviews.

Risk/Benefit Assessment

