Data management and attrition. Participant identifying information will be stored in a secure study database. It will not be stored with questionnaire data to protect patient confidentiality. We anticipate approximately 26% attrition from baseline to immediately post-intervention based on previous supportive care interventions in people with cancer. ⁹⁰ Therefore, we will recruit approximately 38 participants to obtain full data from 30 participants. Reasons for withdrawal will be collected when possible. Data will be checked on an ongoing basis for completeness. If data are determined to be missing systematically, we will consider statistical approaches to manage data missingness (i.e., data imputation methods). [name] will work with statistical experts to determine the most appropriate methods for handling missing data. **ii.**

Statistical Power. Phase 1 will include 4-6 focus groups of approximately 5 patient stakeholders each (N=20), and individual interviews with thoracic oncology providers (N=6) and palliative care, survivorship and behavioral symptom management experts (N=6). Assuming the same potential rate of attrition for focus groups due to scheduling conflicts, illness, etc., we will recruit up to 26 participants to get focus group data from 20 participants (assuming 26% attrition). For Phase 2, we will recruit up to 38 participants to get complete data on approximately 30 participants (assuming 26% attrition). These numbers were calculated based off of relevant literature and work that has been previously successfully completed in this setting. 64,90 Literature suggests that 2-3 focus groups are necessary to reveal 80% of qualitative themes.

Analytic Plan.

Aim 1: Adapt Intervention. In-depth interviews and focus groups will be transcribed verbatim using QSR NVivo software. Data analyses will be based on a grounded theory approach, which has been used in the development of other psychosocial interventions for patients with cancer. ⁹² [name] will complete several workshops on analyzing qualitative data (see Training Plan). Additionally, the PI and members of the mentoring team have experience with qualitative data analyses. [name] is a member of the Cancer Control and Population Sciences Program at DUMC, which has a shared resource of qualitative analytic experts. Experts will be consulted as necessary to ensure appropriate handling and conducting of qualitative analyses.

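### Acceptability is rated only post-intervention, about 26% attrition is expected by then, and the plan does not seek a satisfaction rating from patients who discontinue

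*Combined protocol and SAP*

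**What the plan says.** All references are to the combined protocol and SAP.

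- **Measure and timing** (Study Interventions, item c): "Acceptability will be assessed post-intervention using the 8-item Client Satisfaction Questionnaire (CSQ").
- **Criterion** (same item): "Acceptability will be demonstrated by 80% of participants reporting intervention satisfaction on the CSQ". The Aim 2 analytic plan repeats the 80% figure. Neither place says whether participants means those enrolled, those who started, or those who returned a CSQ.
- **Expected loss** (Data management and attrition): "We anticipate approximately 26% attrition from baseline to immediately post-intervention". The same paragraph plans about 38 recruits to obtain 30 with full data, and says imputation will be considered if data prove to be missing systematically.
- **Information from leavers**: "Reasons for missed sessions and study discontinuation will be collected" (Study Interventions, item b) and "Reasons for withdrawal will be collected when possible" (Data management and attrition).
- **Exit interview**: Subject Recruitment and Compensation and Study Interventions, item e, both say: "All participants will be offered the opportunity to participate in a qualitative exit interview after completing the post-intervention assessment". The Phase 2 text in Design & Procedures also promises the offer to every participant, but attaches no timing.
- **Analysis set** (Aim 2 analytic plan): "Analyses will be conducted using an intent-to-treat approach to include all available data", up to 38 patients.

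**The concern.** The CSQ is the only acceptability measure with a success threshold. It is taken at the end of the interval over which the plan expects to lose about a quarter of its patients. A reason for leaving is recorded, but a reason is not a satisfaction score and cannot enter the 80% criterion. The rate will therefore rest mainly on patients who stay.

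The Background says that initial evidence of feasibility, acceptability and improvement would lead to a larger randomised trial, and exit interviews are meant to refine the intervention. If patients who disliked the programme are under-represented among raters, the satisfaction rate looks better than it is and the refinement misses the people it could learn most from.

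**Working it through.** **1. How many patients could be unrated.** The plan's inputs are 38 recruits, 30 with full data, and 26% attrition.

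- The stated 38 is reproduced by 30 × 1.26 = 37.8. Allowing for 26% loss in the usual way gives 30/0.74 = 40.5, so 41. This side point does not affect what follows.
- Taking 38 as given, 26% loss leaves 38 × 0.74 = 28.1, so about 28 raters and 10 unrated. The plan's own target leaves 30 raters and 8 unrated (8/38 = 21.1%).

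**2. What a passing result leaves open.** This step needs no assumption about why patients leave. It supposes only that those lost give no CSQ.

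- Lost: 9/38 = 23.7%, within the 25% attrition limit.
- Satisfied among raters: 24/29 = 82.8% (exact 95% CI 64.2% to 94.2%), above 80%.
- Among all 38, if none of the 9 was satisfied: 24/38 = 63.2% (46.0% to 78.2%).
- If all 9 were satisfied: 33/38 = 86.8% (71.9% to 95.6%).
- Since 31/38 = 81.6% and 30/38 = 78.9%, the all-patient rate reaches 80% only if at least 7 of the 9 were satisfied.

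The spread is similar at the plan's own figures. The lowest passing result with 28 raters, 23/28 (82.1%), is compatible with 23/38 = 60.5% to 33/38 = 86.8%. With 30 raters, 24/30 (80.0%) is compatible with 63.2% to 32/38 = 84.2%.

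**3. How large a bias could be.** This is an illustration, and every input except the 38 and the loss rate is an assumption.

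Let t be true satisfaction, a the expected loss, and R the dropout rate of dissatisfied relative to satisfied patients. Leavers give no CSQ and the denominator is CSQ responders. Then satisfied patients drop out at d = a/(t + R(1 − t)), and the expected observed rate is t(1 − d)/(1 − a).

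For t = 0.75, a = 0.26 and R = 2: d = 0.26/1.25 = 0.208, and the rate is 0.75 × 0.792/0.74 = 80.3%.

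The last column is the chance of meeting both criteria: at most 9 of 38 lost, and at least 80% of raters satisfied. It is an exact sum with losses binomial(38, a).

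| t | a | Observed rate at R = 1, 2, 3 | Chance of meeting both |
|---|---|---|---|
| 75% | 26% | 75.0%, 80.3%, 83.8% | 13%, 25%, 34% |
| 75% | 21% | 75.0%, 79.0%, 81.7% | 21%, 35%, 46% |
| 70% | 26% | 70.0%, 75.7%, 79.2% | 6%, 14%, 23% |
| 80% | 26% | 80.0%, 84.7%, 88.0% | 24%, 36%, 42% |

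With R = 1 there is no bias. If half of leavers gave a CSQ, the first row's rates would be 75.0%, 77.2% and 78.7%. If all did, the rate would be 75.0% throughout.

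**The case against.** Several points on the other side stand.

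- **A reader might infer that acceptability will be overstated.** The documents do not support that. No passage links dropout to dissatisfaction, and Data & Safety Monitoring expects some hospitalisations and deaths. The ratios of 2 and 3 above are invented; a ratio of 3 means 52% of dissatisfied patients leave against 17% of satisfied ones. Upward bias also presupposes a responders-only denominator. With all 38 as denominator, the example gives 63.2% and fails.
- **A reader might infer that leavers are excluded from the exit interview or barred from the CSQ.** Neither is stated. Design & Procedures promises the interview to all, while the two other passages place it after the post-intervention assessment, so the offer to discontinuers is unclear rather than withheld. Payment is "for completing each of the three study assessments" with no attendance condition, and a patient who stops sessions may still complete the assessment.
- **Dropout is visible elsewhere.** Attrition and attendance are separate criteria, reasons for leaving are collected, and homework completion is recorded. At 26% expected loss the attrition limit is met only 46% of the time, so heavy dropout counts against the intervention whatever the CSQ shows. The calculation above leaves out attendance and accrual, and treats loss from treatment and loss of data as one count.
- **The plan has a missing-data sentence.** It is general and commits only to considering imputation. It does not supply ratings that nobody sought.
- **Early and full-course ratings differ in meaning.** A CSQ after one or two sessions rates a partial programme, so a single pooled figure would be debatable.

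These points limit the claim about bias. They do not remove the gap in what is collected.

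**Conclusion.** The concern holds as a gap in data collection and definition. Acceptability is scored at one late time point, about a quarter of patients may be gone by then, the plan does not seek their rating, and the denominator is not stated. A result that meets both criteria can leave the all-patient rate uncertain by more than 20 percentage points (63.2% to 86.8% in the example), given only that those lost return no CSQ.

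Whether the reported rate would be too high, and by how much, depends on assumptions the documents cannot settle: that dissatisfied patients leave more often, that leavers return no CSQ, and that responders form the denominator. The all-available-data rule makes the last of these likely. Under all three, at 26% loss, dropout twice as common among the dissatisfied would carry a true 75% to an expected 80.3%.

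The criterion is descriptive, the study is a single-arm pilot, and no numerical rule for proceeding to the larger trial is given. This is a modest improvement that should be made, not a flaw that undermines the study.

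**What to change.** 1. Offer the same CSQ, and the exit interview that Design & Procedures already promises to all, at discontinuation to everyone who started the intervention. Align the three exit-interview passages.
2. State the denominator of the 80% criterion: all starters who gave a CSQ, whether post-intervention or at discontinuation. Report the number of raters.
3. Show ratings for completers and discontinuers separately as well as combined, since the latter rate a partial course.
4. Beside the combined rate, report the share of all starters satisfied with a missing CSQ counted as not satisfied. Label it a lower bound. It should not be the criterion, because with 8 or more of 38 unrated it cannot reach 80% (30/38 = 78.9%).
5. Give exact 95% CIs for both, and tabulate missing CSQs by the discontinuation reasons already collected.

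The cost is eight existing items and an optional interview for early leavers, a few table lines, some mixing of partial-course ratings into the combined rate, and possibly a less favourable figure. Patients who die, are too ill or decline will still be unrated, so any bias shrinks only as far as leavers respond.
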